7.6 Outcome Measures:**Primary Outcome:**

The primary outcome is ventilator-free days (VFDs) to day 28 after enrollment.

VFDs will be defined as the number of calendar days alive and free of invasive mechanical ventilation from the final receipt of invasive mechanical ventilation through 28 days after enrollment. Outcome ascertainment will cease at the time of hospital discharge or 28 days after enrollment, whichever occurs first. Receipt of invasive mechanical ventilation will be considered to end when patients undergo the final tracheal extubation or disconnection of the ventilator from a tracheostomy tube between enrollment (day 1) and day 28 after enrollment. Patients who die prior to discharge on or before day 28 will receive zero VFDs. Patients whose final receipt of invasive mechanical ventilation occurs on the day of enrollment and survive to day 28 will receive 27 VFDs. Patients who continue to receive invasive mechanical ventilation at day 28 will receive zero VFDs. Patients who are discharged from the hospital prior to day 28 and are receiving invasive mechanical ventilation at the time of discharge will receive zero VFDs. Patients who are removed from invasive mechanical ventilation and are discharged from the hospital without invasive mechanical ventilation prior to 28 days will be assumed to remain alive and

free of invasive mechanical ventilation between hospital discharge and day 28. For patients who are removed from invasive mechanical ventilation, return to invasive mechanical ventilation, and are subsequently removed again from invasive mechanical ventilation prior to day 28, VFDs will be counted from the final receipt of invasive mechanical ventilation prior to day 28.

Feasibility Outcomes

- Exposure to assigned study mode in first 3 days: proportion of time in the assigned mode while receiving invasive mechanical ventilation in the study ICU between enrollment and 72 hours after enrollment.
- Adherence to study mode in first 3 days: proportion of time in the assigned mode while receiving invasive mechanical ventilation in the study ICU with a mandatory mode between enrollment and 72 hours after enrollment (excluding time spent in spontaneous modes).
- Time from enrollment to initiation of assigned mode of mechanical ventilation
- Receipt of a "Mode Modification Sheet" completed by treating clinicians

Exploratory Efficacy and Safety Outcomes

- Median exhaled tidal volume (mL/kg predicted body weight (PBW)) on each study day
- Exhaled tidal volumes above target range: proportion of recorded breaths with exhaled tidal volume values above the target range ($> 8\text{mL/kg PBW}$) on each study day
- Hypoxemia during mechanical ventilation: episodes of hypoxemia during mechanical ventilation: $\text{SpO}_2 < 85\%$ for more than 5 minutes
- Severe acidemia during mechanical ventilation: Episodes of severe acidemia during mechanical ventilation: $\text{pH} < 7.1$ on blood gas
- Number of blood gas laboratory tests per day while receiving mechanical ventilation
- Pneumomediastinum or pneumothorax during course of mechanical ventilation
- SOFA score daily on the first 7 study days
- Delirium and coma-free days to day 28

Exploratory Clinical Outcomes:

- ICU-free days to study day 28
- Hospital-free days to study day 28
- In-hospital mortality to study day 28

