Enrollment (Day 0): date and time of clinical events (hospital admission, ICU admission, intubation); source of admission to study ICU; age; sex; race; ethnicity; height, weight;⁶⁴ SOFA score;⁶⁵ Glasgow Coma Scale score;⁶⁶ Elixhauser Comorbidity Index;⁶⁷ history of present illness; vital signs (temperature, heart rate, systolic blood pressure, diastolic blood pressure, SpO₂); mechanical ventilator settings (mode, set and exhaled tidal volumes, set and actual respiratory rate, minute ventilation, set and total positive end-expiratory pressure, peak pressure, plateau pressure, inspiratory time, flow pattern, FiO₂); serum laboratory values (white blood cell count, hemoglobin, platelet count, sodium, potassium, bicarbonate, creatinine, bilirubin, alanine aminotransferase, aspartate aminotransferase, lactate, arterial and venous pH, PaCO₂, PaO₂, SaO₂).

Daily On-Study (Days 0-28): Vital signs, ventilator settings, screening for and performance of spontaneous awakening trials and spontaneous breathing trials, and serum laboratory values (as above); Mean daily dose of sedative infusions (propofol, dexmedetomidine, morphine, fentanyl, and midazolam); CAM status; RASS score; Daily completion of each element from ICU Liberation Bundle (A-F); Beginning and end time of Spontaneous Breathing Trials; vasopressor and inotrope infusions (norepinephrine, epinephrine, vasopressin, phenylephrine, dobutamine, angiotensin-2, dopamine); “Mode Modification Sheet” (use, time, reason); Characteristics of treating clinicians (respiratory therapist, attending, pulmonary fellow, registered nurse) providing direct care; Use of therapies for refractory hypoxemia (prone positioning, ECMO, neuromuscular blockade, inhaled pulmonary dilators); SOFA score; ARDS criteria by the Berlin Definition;⁶⁸ Stage II or greater AKI by KDIGO criteria;⁶⁹ cardiac arrest, pneumothorax or pneumomediastinum.

Termination (Days 0-28): Vital status at 28 days; time of liberation from invasive mechanical ventilation; receipt and duration of vasopressors; receipt and duration of renal replacement therapy; tracheostomy; duration of ICU and hospital admission.

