10.0 Statistical Considerations

Sample size justification.

The purpose of this trial is to assess feasibility of a cluster-randomized, cluster-crossover design. To assess whether compliance can be maintained after cross-over events, we will need to observe two cross-over events to each mode while maintaining an equal number of treatment blocks for each mode. Doing so will require a total of 9 months. Based on the experience of a prior trial in the same ICU,⁷⁰ we anticipate an average of 75 patients on mechanical ventilation will be enrolled per month. In 9 months, we expect to enroll 675 patients, of whom 69 will be enrolled during washout periods and excluded from the primary analysis. The resulting 606 patients will be included in the primary analysis.

While the sample size was determined to demonstrate feasibility of the cluster-crossover design, we anticipate this pilot will be the largest randomized trial of ventilator modes to date, and as such, we plan to compare ventilator free days to day 28 (primary outcome) between groups. In a prior cluster-randomized cluster-crossover trial in the same ICU,⁷⁰ mechanically ventilated patients experienced a median of 22 VFDs [IQR 0-25 VFDs] and an intra-cluster intra-period correlation of 0.01. With 606 (202 in each group) patients in the primary analysis, a standard deviation in the primary outcome of VFDs of 11 days, and a two-sided alpha of 0.05, the MODE trial will have 80 percent statistical power to detect an absolute difference between groups in the sole primary clinical endpoint of Ventilator Free Days of 3 days.

Primary Analysis of the Primary Clinical Outcome

The sole pre-specified primary outcome of ventilator free days will be compared between the three trial groups in an intention-to-treat fashion among all patients enrolled in the trial except those admitted during one of the 3-day washout periods. To estimate the conditional effect of a group assignment on an individual patient given the values of the covariates for that patient, we will use a proportional odds model with independent covariates of group assignment (volume control, pressure control, or adaptive

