12.0 Follow-up and Record Retention

Patients will be followed after enrollment for 28 days or until hospital discharge, whichever occurs first. Data collected from the medical record will be entered into the secure online database REDCap. Hard copies of the treating clinician Mode Modification Sheet will be used for manual data entry into the REDCap database and stored in a locked room until after the completion of enrollment and data cleaning. All data will be maintained in the secure online database REDCap until the time of study publication. Once data are verified and the database is locked, all hard copies of Mode Modification Sheets will be destroyed. At the time of publication, a de-identified version of the database will be generated.

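### The ventilator-free-day rule assumes every patient discharged off the ventilator survives to day 28, so an early discharge to hospice can score above the planning upper quartile

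*Combined protocol and SAP*

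**What the plan says.** Section 7.6 defines the primary outcome and gives zero VFDs in three situations:

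- death in hospital: "Patients who die prior to discharge on or before day 28 will receive zero VFDs";
- ventilation still continuing at day 28;
- discharge before day 28 on a ventilator: those who "are receiving invasive mechanical ventilation at the time of discharge will receive zero VFDs".

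Everyone else who leaves hospital early falls under one assumption. Patients "discharged from the hospital without invasive mechanical ventilation prior to 28 days will be assumed to remain alive" and off the ventilator until day 28. Where they are discharged to plays no part, and hospice is not mentioned anywhere in the document.

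The top of the scale is fixed by this rule: "Patients whose final receipt of invasive mechanical ventilation occurs on the day of enrollment and survive to day 28 will receive 27 VFDs".

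On follow-up, 7.6 states: "Outcome ascertainment will cease at the time of hospital discharge or 28 days after enrollment, whichever occurs first". Section 12.0 agrees: "Patients will be followed after enrollment for 28 days or until hospital discharge, whichever occurs first". Section 7.5, however, lists among the termination data "Vital status at 28 days; time of liberation from invasive mechanical ventilation".

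Section 10.0 plans two sensitivity analyses of the primary outcome: adjustment for baseline covariates, and inclusion of patients from the washout periods. It expects no missing primary outcome data.

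**The concern.** The clinical aim in Section 3.1 is survival without the ventilator, and a death in hospital takes the lowest score. Under the 7.6 rule, a death shortly after discharge can take one of the highest. Patients whose ventilator is withdrawn for comfort and who then leave for hospice are the clearest case: removal may be early, and survival to day 28 is doubtful.

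The plan already treats one kind of discharge as a poor outcome, since leaving on a ventilator scores zero. It does not do so for the other obvious poor-prognosis discharge. The expectation of complete primary outcome data rests, for discharged patients, on the survival assumption and not on observation.

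At stake is how faithfully the primary outcome reflects its own definition and, if the frequency of such discharges differs between modes, the comparison itself. Removal of the ventilator and discharge are decided by clinicians who know the assigned mode (Section 7.4).

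**Working it through.** **1. The plan's own figures.** Section 10.0 gives 202 patients per group, SD 11 days, two-sided alpha 0.05 and 80% power for a 3-day difference. With no allowance for clustering, the detectable difference is (1.960 + 0.842) × 11 × √(2/202) = 3.07 days, and power at 3 days is 0.783. The stated figure is reproduced to rounding. It is used below only as a yardstick; the present point does not change it.

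**2. Score by last ventilated day.** Section 7.6 counts enrollment as day 1 and gives 27 VFDs when ventilation last occurs on that day, so VFDs = 28 − *d*, where *d* is the last ventilated day. The planning distribution in Section 10.0, from a prior trial in the same ICU, has median 22 and quartiles 0 and 25.

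| Last ventilated day *d* | Discharged off ventilator (28 − *d*) | Dies in hospital by day 28 | Discharged score against planning distribution |
|---|---|---|---|
| 1 | 27 | 0 | above upper quartile |
| 2 | 26 | 0 | above upper quartile |
| 3 | 25 | 0 | equals upper quartile |
| 4 | 24 | 0 | above median |
| 5 | 23 | 0 | above median |
| 6 | 22 | 0 | equals median |
| 7 | 21 | 0 | below median |

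For example, a patient extubated on day 2, discharged to hospice on day 3 and dead on day 5 scores 26. The same patient kept in hospital and dying on day 5 scores 0.

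**3. Possible effect on a group mean.** The documents give no rate of discharge to hospice and no distribution of last ventilated day among such patients. Both inputs here are assumptions: a share *h* of a group is affected, each scoring *v* where zero would otherwise apply. The shift in the group mean is *h* × *v*.

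| *h* (assumed) | Patients of 202 | *v* = 20 | *v* = 27 |
|---|---|---|---|
| 1% | about 2 | 0.20 days | 0.27 days |
| 3% | about 6 | 0.60 days | 0.81 days |
| 5% | about 10 | 1.00 days | 1.35 days |
| 8% | about 16 | 1.60 days | 2.16 days |

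The range is roughly 0.2 to 2.2 days. A score of 20 corresponds to last ventilation on day 8, which is below the planning median, so the low column does not describe the early-removal patients in step 2.

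**4. Effect on the contrast.** If share and score are the same in every group, the shift in means is the same and cancels. The imbalance that would by itself produce a 3-day difference is 3/*v*: 3/20 = 15 percentage points, 3/25 = 12, or 3/27 = 11. A 3-point imbalance would give 0.03 × 20 = 0.6 to 0.03 × 27 = 0.8 days.

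**5. Scale.** The primary analysis is a proportional odds model, so these mean shifts are a guide to size and do not convert directly to the planned odds ratio. What carries over is the ordering: the affected patients move from the bottom category to a high one.

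**The case against.** The strongest reply is that the rule is explicit and pre-specified, and nothing in the VFD scoring contradicts itself. The trial is a feasibility pilot whose sample size was not set by this outcome. The proposed fix replaces one assumption with another, since some hospice patients live past day 28. It also relies on discharge disposition, which is not among the elements listed in 7.5 and is itself influenced by unblinded clinicians. All of that is fair. It makes this a weakness of definition and not an error, and it makes a sensitivity analysis an acceptable minimum. It does not answer the mis-scoring, which follows from the rule whatever the hospice rate.

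Four stronger readings are tempting and are not supported:

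- *The comparison is biased.* The documents give no reason to expect mode to change the frequency of hospice discharge. Differences between months are partly handled by permuted blocks of 3 and by the spline for calendar time.
- *In-hospital mortality is flattered too.* That outcome counts deaths in hospital by definition and assumes nothing about survival afterwards.
- *ICU-free and hospital-free days share the flaw.* No scoring rule is written for them, so this cannot be said.
- *Day-28 vital status is not obtained after discharge.* Section 7.5 lists it. What can be said is that 7.5 is not reconciled with 7.6 and 12.0, and that the VFD rule makes no use of the item after discharge.

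**Conclusion.** The concern stands as a weakness in the definition of the primary outcome. By the plan's own arithmetic, a patient last ventilated on day 1 or 2 and discharged to hospice scores 27 or 26, above the planning upper quartile; removal on days 3 to 5 still beats the median. No planned analysis would reveal how much this matters.

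Its size cannot be computed from the documents. The range of 0.2 to 2.2 days rests on assumed shares of 1–8% and assumed scores of 20–27, on the mean scale. The quartiles come from an earlier trial in the same ICU and not from this one. A reader might infer that the rule could manufacture the 3-day target difference; that would need an imbalance of about 11 to 15 percentage points between modes, for which the documents offer no basis. The change is worth making because it is cheap and because this pilot is meant to inform a larger trial.

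**What to change.** 1. Add to 7.6: *Patients discharged to hospice on or before day 28 receive zero ventilator-free days.* Take discharge disposition from the EHR or the registration data already named as sources in 7.5, and add it to the list of extracted elements. If the primary definition is to stay as it is, pre-specify this scoring as a sensitivity analysis of the primary outcome.
2. Add a sensitivity analysis that uses day-28 vital status, where recorded, in place of the survival assumption.
3. Reconcile 7.5 with 7.6 and 12.0: state whether day-28 vital status is sought for discharged patients and, if so, from which source.

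The cost is one scoring sentence, one data field that the existing feeds could plausibly supply, and one or two further fits of a model already planned. The downside is that a few hospice patients who live beyond day 28 would be scored as deaths; the vital-status analysis would show how many, where the status is recorded.

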8.0 Risks and Benefits

Although no risks are currently known to differ between mechanical ventilation with volume control, pressure control, and adaptive pressure control (all standard-of-care approaches in currently clinical care), it is possible that the results of the MODE trial will ultimately demonstrate a difference between the approaches in the risk of ventilator-free days, hypoxemia, delirium and coma free days, or another outcome. The benefits of this research will include understanding the effect of choice of ventilator mode on outcomes for the 2-3 million adults per year who receive invasive ventilation.

9.0 Safety Monitoring and Adverse Events

Assuring patient safety is an essential component of this protocol. Mechanical ventilation with volume control, pressure control, and adaptive pressure control are all standard-of-care interventions that have been use in clinical practice for decades with an established safety profile. This protocol further ensures safety of its participants through:

- a. Exclusion criteria designed to prevent enrollment of patients likely to experience adverse events from pressure control, volume control, or adaptive pressure control settings;
- b. Permitting treating clinicians to change the ventilator mode at any time for any patient in whom they feel a ventilator mode different from the assigned mode is required for the safe treatment of the patient;
- c. Systematic collection of outcomes relevant to the safety of ventilator mode selection;
- d. Structured monitoring, assessment, recording, and reporting of adverse events.

9.1 Adverse Event Definitions:

Adverse Event – An adverse event will be defined as any untoward or unfavorable medical occurrence in a human subject temporally associated with the subject’s participation in the research, whether or not considered related to the subject’s participation in the research. Adverse events will be classified according to the following characteristics:

- **Seriousness** – An adverse event will be considered “serious” if it:
 - Results in death;
 - Is life-threatening (defined as placing the patient at immediate risk of death);
 - Results in inpatient hospitalization or prolongation of existing hospitalization;
 - Results in a persistent or significant disability or incapacity;
 - Results in a congenital anomaly or birth defect; or
 - Based upon appropriate medical judgment, may jeopardize the patient’s health and may require medical or surgical intervention to prevent one of the other outcomes listed in this definition.
- **Unexpectedness** – An adverse event will be considered “unexpected” if the nature, severity, or frequency is neither consistent with:
 - The known or foreseeable risk of adverse events associated with the procedures involved in the research that are described in the protocol-related documents, such as the IRB-approved research protocol; nor
 - The expected natural progression of any underlying disease, disorder, or condition of the subject experiencing the adverse event and the subject’s predisposing risk factor profile for the adverse event.
- **Relatedness** – The strength of the relationship of an adverse event to a study intervention or study procedure will be defined as follows:
 - Definitely Related: The adverse event follows (1) a reasonable, temporal sequence from a study procedure AND (2) cannot be explained by the known characteristics of the patient’s clinical state or other therapies AND (3) evaluation of the patient’s clinical state indicates to the investigator that the experience is definitely related to study procedures.
 - Probably or Possibly Related: The adverse event meets some but not all of the above

criteria for “Definitely Related”.

- Probably Not Related: The adverse event occurred while the patient was on the study but can reasonably be explained by the known characteristics of the patient’s clinical state or other therapies.
- Definitely Not Related: The adverse event is definitely produced by the patient’s clinical state or by other modes of therapy administered to the patient.
- Uncertain Relationship: The adverse event does not fit in any of the above categories.

9.2 Monitoring for Adverse Events:

For patients whose mode of mechanical ventilation is controlled by the trial, investigators will evaluate for the occurrence of adverse events daily as part of the assessment of ventilator modes. Investigators will assess any adverse events that occur for whether the adverse event meets the criteria for recording and reporting outlined below.

9.3 Recording and Reporting Adverse Events:

The following types of adverse events will be recorded and reported:

- Adverse events that are Serious and Definitely Related, Probably or Possibly Related, or of Uncertain Relationship.
- Adverse events that are Unexpected and Definitely Related, Probably or Possibly Related, or of Uncertain Relationship.

Adverse events that do not meet the above criteria will not be recorded or reported. Adverse events that the investigator assesses to meet the above criteria for recording and reporting will be entered into the adverse event electronic case report form in the trial database. The investigator will record a preliminary assessment of each characteristic for the adverse event, including seriousness, unexpectedness, and relatedness. For any adverse event that is **serious AND unexpected**, and definitely related, probably or possibly related, or of uncertain relationship, the investigator will report the adverse event to the principal investigator **within 24 hours** of the investigator becoming aware of the adverse event. For any other adverse event requiring recording and reporting, the investigator will report the adverse event to the principal investigator **within 72 hours** of the investigator becoming aware of the adverse event. The principal investigator will make the final determination regarding each characteristic for the adverse event, including seriousness, unexpectedness, and relatedness.

For adverse events that meet the above criteria for recording and reporting, the coordinating center will notify the DSMB, the IRB, and the sponsor in accordance with the following reporting plan:

Characteristics of the Adverse Event	Reporting Period
Fatal or life-threatening (and therefore serious), unexpected, and definitely related, probably or possibility related, or of uncertain relationship.	Report to DSMB and IRB within 7 days after notification of the event.

Serious but non-fatal and non-life-threatening, unexpected, and definitely related, probably or possibly related, or of uncertain relationship.	Report to DSMB and IRB within 7 days of notification of the event.
All other adverse events meeting criteria for recording and reporting.	Report to DSMB and IRB as part of continuing review.

The investigator will distribute the written summary of the DSMB's periodic review of reported adverse events to the IRB in accordance with NIH guidelines (<http://grants.nih.gov/grants/guide/notice-files/not99-107.html>).

9.4 Clinical Outcomes that may be Exempt from Adverse Event Recording and Reporting:

In this study of critically ill patients at high risk for death and other adverse outcomes due to their underlying critical illness, clinical outcomes, including death and organ dysfunction, will be systematically collected and analyzed for all patients. The primary and exploratory outcomes will be recorded and reported as clinical outcomes and not as adverse events unless treating clinicians or site investigators believe the event is Definitely Related or Probably or Possibly Related to the study intervention or study procedures. This approach – considering death and organ dysfunction as clinical outcomes rather than adverse events and systematically collecting these clinical outcomes for analysis – is common in ICU trials. This approach ensures comprehensive data on death and organ dysfunction for all patients, rather than relying on sporadic adverse event reporting to identify these important events. The following events are examples of study-specific clinical outcomes that would not be recorded and reported as adverse events unless treating clinicians or site investigators believe the event was Definitely Related or Probably or Possibly Related to the study intervention or study procedures:

- Death (all deaths occurring prior to hospital discharge or 28 days will be recorded);
- Organ dysfunction
 - Pulmonary – hypoxemia, hypercarbia, acute hypoxemic respiratory failure, pneumothorax;
 - Cardiac – hypotension, cardiac arrest or shock with or without receipt of vasopressors;
 - Delirium or coma;
- Duration of mechanical ventilation;
- Duration of ICU admission;
- Duration of hospitalization.

Note: A study-specific clinical outcome may also qualify as an adverse event meeting criteria for recording and reporting. For example, a pneumothorax that the investigator considers Definitely Related to ventilator mode would be both recorded as a study-specific clinical outcome and recorded and reported as a Serious and Definitely Related adverse event.

9.5 Unanticipated Problems Involving Risks to Subjects or Others:

Investigators must also report to the principal investigator Unanticipated Problems Involving Risks to Subjects or Others (“Unanticipated Problems”), regardless of severity, associated with study procedures

within 24 hours of the investigator becoming aware of the Unanticipated Problem. An Unanticipated Problem is defined as any incident, experience, or outcome that meets all of the following criteria:

- Unexpected (in terms of nature, severity, or frequency) given (a) the research procedures that are described in the protocol-related documents, such as the IRB-approved research protocol; and (b) the characteristics of the subject population being studied; AND
- Definitely Related or Probably or Possibly Related to participation in the research (as defined above in the section on characteristics of adverse events); AND
- Suggests that the research places subjects or others at a greater risk of harm (including physical, psychological, economic, or social harm) than was previously known or recognized.

Upon becoming aware of any event that may represent an Unanticipated Problem, the investigator will assess whether the event represents an Unanticipated Problem by applying the criteria described above. If the investigator determines that the event represents an Unanticipated Problem, the investigator will record the Unanticipated Problem in the Unanticipated Problem electronic case report form in the trial database. The investigators will obtain information about the Unanticipated Problem and report the Unanticipated Problem to the DSMB and the IRB within 15 days of becoming aware of the Unanticipated Problem.

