Additionally, mechanical ventilation can damage lungs even after brief periods of ventilation, and the initial settings have a unique significance. For example, during the minutes-to-hours of temporary mechanical ventilation for surgical procedures, harmful ventilator settings can affect organ function and clinical outcomes.³⁴ In critically ill patients, the initial hours of invasive mechanical ventilation are also the period with the highest risk of worsening lung injury, dyssynchrony, increased work of breathing, and hemodynamic compromise. Prior research has demonstrated that [1] the very first ventilator settings at the time the patient is being initiated on invasive mechanical ventilation in the ICU are associated with differences in mortality^{35,36} and [2] the association between ventilator settings and mortality is larger for earlier settings compared to later settings.³³ The ventilator protocol used to set the ventilator mode in the study ICU begins immediately at the time of initiation of mechanical ventilation. Enrollment immediately after initiation of invasive mechanical ventilation minimizes pre-study exposure to other modes and ventilator settings, and it facilitates on-study separation between groups.

Recognizing the importance of initial ventilator settings, three recent clinical trials have examined other ventilator settings (i.e. end-expiratory pressure, tidal volume, and SpO₂ target) by attempting to enroll patients soon after the initiation of mechanical ventilation in the ICU.^{12,37,38} In these patient-level, parallel-group trials, however, the logistical challenges of performing screening, enrollment, randomization, and study group assignment resulted in a significant gap between initiation of invasive mechanical ventilation and delivery of the respective trial interventions while also leading to the exclusion of 60-67% of eligible patients – raising concern for systematic exclusion of important patient groups (e.g. patients with higher acuity of illness). In MODE, group assignment at the cluster level allows enrollment immediately on initiation of invasive mechanical ventilation in the ICU. This approach emulates the manner in which ventilator settings are managed in practice, precludes systematic exclusion of important patient groups, decreases pre-study exposure to harmful ventilator settings, and facilitates early separation in the receipt of ventilator modes between groups.

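### Under 9.4, cardiac arrest, shock, hypotension and hypercarbia are exempt from adverse-event recording unless judged at least possibly related, yet none is a listed outcome, and 9.4 omits the Uncertain Relationship category that 9.3 includes

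*Combined protocol and SAP*

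**What the plan says.** Section 9.3 sets the general rule. One of its two reportable classes is "Adverse events that are Serious and Definitely Related, Probably or Possibly Related, or of Uncertain Relationship"; the other applies the same three relatedness categories to unexpected events. Anything outside these classes is not recorded as an adverse event.

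Section 9.4 then carves out study-specific clinical outcomes. Its justification is that "clinical outcomes, including death and organ dysfunction, will be systematically collected and analyzed for all patients". The pulmonary examples are "hypoxemia, hypercarbia, acute hypoxemic respiratory failure, pneumothorax", and the cardiac examples are "hypotension, cardiac arrest or shock with or without receipt of vasopressors". Such events stay out of the adverse-event record, with this exception: "unless treating clinicians or site investigators believe the event was Definitely Related or Probably or Possibly Related to the study intervention". The exception covers the trial's procedures as well. A note adds that an event may go by both routes, and illustrates this with a Definitely Related pneumothorax.

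Section 7.6 lists the outcomes. Hypoxemia is there, and so is "Pneumomediastinum or pneumothorax during course of mechanical ventilation". Section 10.0 plans between-group comparisons of the listed exploratory outcomes. It gives the DSMB three interim safety outcomes: pneumomediastinum or pneumothorax, hypoxemia, and in-hospital mortality.

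**The concern.** An exemption of this kind is common in ICU trials and is sound when every exempted event is counted as an outcome and compared between groups. The comparison then replaces case-by-case attribution. If an exempted event is not an outcome, nothing replaces the adverse-event record, and detection depends on someone judging the individual event to be related.

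That is a weak safeguard here. Clinicians are unblinded (section 7.4), the patients are critically ill, and each event may be put down to the underlying illness even when one mode has more of them. Section 9.4 itself argues against relying on sporadic adverse-event reports. Section 4.1 describes the first hours of ventilation as the period of "highest risk of worsening lung injury, dyssynchrony, increased work of breathing, and hemodynamic compromise", and section 10.0 lets the DSMB consider stopping a single arm. Its specified interim comparison has no direct circulatory or carbon dioxide measure.

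**Working it through.** The plan gives no figure on this point, so the check sets the sections side by side.

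**Step 1. Are the exempted events outcomes?** Inputs: the list in 9.4, the outcomes in 7.6, the interim outcomes in 10.0 and the data elements in 7.5.

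| Event in 9.4 | Outcome in 7.6 | Interim outcome in 10.0 | Data extracted under 7.5 | Nearest listed outcome |
|---|---|---|---|---|
| Hypercarbia | No | No | PaCO₂ | pH < 7.1 |
| Hypotension | No | No | Blood pressure | Daily SOFA to day 7 |
| Cardiac arrest | No | No | Yes, by name | In-hospital mortality, if fatal |
| Shock | No | No | Vasopressor and inotrope infusions; receipt and duration of vasopressors | Daily SOFA to day 7 |

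Result: 0 of 4 are outcomes, 0 of 4 are interim outcomes, and the data for all 4 are extracted or can be derived. By contrast, hypoxemia and pneumothorax, from the same 9.4 list, are both outcomes and interim items. Section 7.5 extracts cardiac arrest alongside pneumothorax and pneumomediastinum, but only the latter two become an outcome.

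The cover from the nearest outcomes is indirect. A pH threshold is not a PaCO₂ measure. SOFA is a composite that stops at day 7, and that it reflects hypotension or vasopressor use is an assumption, because the protocol does not give its components. Mortality captures only fatal arrests.

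**Step 2. Which relatedness judgements keep the adverse-event route open?** Inputs: the five categories in 9.1, applied to a serious or unexpected event on the 9.4 list.

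| Relatedness | Reportable under 9.3 | Reportable under 9.4 |
|---|---|---|
| Definitely Related | Yes | Yes |
| Probably or Possibly Related | Yes | Yes |
| Uncertain Relationship | Yes | No |
| Probably Not Related | No | No |
| Definitely Not Related | No | No |

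Result: 3 of 5 under 9.3 and 2 of 5 under 9.4. The sections conflict in one category. The 9.4 note does not settle it, since its only example is Definitely Related. Section 9.5 is no backstop, because an Unanticipated Problem must also be at least Probably or Possibly Related.

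**Step 3. Combine the two.** Take a non-fatal cardiac arrest classed as Uncertain Relationship. Under 9.3 it is serious, so it is recorded. It goes to the DSMB and IRB within 7 days if also unexpected, and otherwise at continuing review. Under 9.4 it is not recorded as an adverse event. Under 7.6 and 10.0 it enters no named comparison. For the two not-related categories 9.4 removes nothing that 9.3 would have kept. There the gap is only the missing comparison between modes.

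**The case against.** The strongest reply is that little is actually lost.

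- A reader might infer that 9.4 takes these events out of adverse-event reporting altogether. It does not. The section heading says they may be exempt, and the belief of either a treating clinician or a site investigator that the event is at least possibly related is enough to keep it reportable.
- Under 9.1, meeting some of the criteria for a definite relationship makes an event Probably or Possibly Related, and one criterion is a reasonable temporal sequence. An arrest soon after the assigned mode starts would often qualify. Uncertain Relationship is a residual class, and nothing in the protocol shows that it is common.
- A reader might infer that the data are lost. They are extracted under 7.5. The gap lies in the outcome list, the analysis and the specified DSMB review.
- A reader might infer that the DSMB would never see these events. That cannot be shown. The interim analysis comes on top of continuing safety monitoring, section 13.0 has the DSMB review data regularly under its own charter, and that charter is not among the documents.
- Section 4.1 does not say that hemodynamic risk differs by mode, and section 6.4 says no differences in risk are established.

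All of this stands, and it limits the point. It does not close the conflict over Uncertain Relationship, nor does it supply the analysis on which 9.4 rests its exemption. Extraction without a named outcome leaves any comparison to later choice, and the protocol does not require the DSMB to ask for one.

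**Conclusion.** The point holds in a limited form. For hypercarbia, hypotension, cardiac arrest and shock, the stated ground for the exemption is met for collection but not for direct, prespecified analysis. Events not judged at least possibly related reach neither adverse-event reporting nor a named comparison between modes. These include serious events of Uncertain Relationship that 9.3 requires to be recorded and reported.

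The size is structural: 0 of 4 events with a direct comparison, and one relatedness category on which 9.3 and 9.4 disagree. The protocol gives no event rates and no frequency for the category, so a count of affected patients would be guesswork and none is offered. The conclusion assumes that the specific wording of 9.4 is followed over the general rule in 9.3, and that the DSMB charter does not already ask for these tables. It does not imply that any mode is expected to cause more of these events. The change is worth making because it concerns safety and costs almost nothing.

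**What to change.** 1. Reconcile 9.3 and 9.4 so that serious or unexpected events of Uncertain Relationship that are not 7.6 outcomes are still recorded and reported. Either limit the exemption to events listed in 7.6, or add the missing category to both statements of the exception in 9.4.
2. Add two exploratory safety outcomes to 7.6 from data already extracted: cardiac arrest after enrollment, and new receipt of vasopressors after enrollment. Define the second so that patients already on vasopressors at enrollment are handled explicitly.
3. Show both as descriptive rows by mode in the DSMB interim table, with no new stopping boundary. The 0.016 threshold, set by dividing 0.05 by three outcomes, then stays as it is.
4. Highest daily PaCO₂ is optional. It is seen only when a blood gas is drawn, and the number of gases per day is itself an outcome that may differ by mode.

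The cost is wording in 7.6, 9.4 and 10.0 and a few table rows, with no new data collection. The small downside is a few more descriptive comparisons, which section 10.0 already treats as estimates with 95% confidence intervals and no multiplicity correction.
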